7.3.1.1 Conditions Not Requiring Dose Reduction

The following conditions are exceptions to the above guidelines.

- Grade 3 nausea, vomiting, or diarrhea (unless persisting more than 3 days with adequate treatment of antiemetics or antidiarrheal agents)
- Grade 3 dexamethasone-related hyperglycemia (see Table 6-8 for guidelines and treatment)

- Grade 1-2 lenalidomide and/or ixazomib-induced rash
- Grade 3 fatigue (unless persisting for > 14 days)
- Alopecia

7.4 Mandatory Concomitant Medications

7.4.1 Recommended Concomitant Medications

- Aspirin for VTE prophylaxis.
 - Note: If a subject is allergic to aspirin, low-molecular-weight heparin or clopidogrel may be used. In subjects with a prior history of venous thrombosis, low-molecular-weight heparin or therapeutic doses of warfarin (target INR 2-3) are required (or follow most current guidelines for DVT prophylaxis).
- Acyclovir 400 mg orally twice a day for HZV prophylaxis (or equivalent)

7.4.2 Excluded Concomitant Medications

Concurrent therapy with a marketed or investigational anticancer therapeutic is not allowed.

Corticosteroids for non-malignant conditions (e.g., asthma, inflammatory bowel disease) equivalent to a dexamethasone dose ≥ 4 mg/day or prednisone ≥ 20 mg/day are not permitted.

Other investigational agents are not to be used during the study.

The following medications and procedures are prohibited during the study.

Systemic treatment with any of the following metabolizing enzyme inducers should be avoided, unless there is no appropriate alternative medication for the patient's use (Rationale: If there were to be a DDI with an inducer, ixazomib exposure would be less; therefore, there would be a reduced chance of an AE. However, there may be less chance for an antitumor effect, but that is not an absolute reason to be taken off ixazomib):

- Strong CYP3A inducers: rifampin, rifapentine, rifabutin, carbamazepine, phenytoin, and phenobarbital
- Excluded foods and dietary supplements include St. John's wort and Ginkgo biloba

The following procedures are prohibited during the study.

- Any antineoplastic treatment with activity against MM, other than study drugs
- Radiation therapy (note that, in general, the requirement for local radiation therapy indicates disease progression)
- Platelet transfusions to help patients meet eligibility criteria are not allowed within 3 days prior to study drug dosing for any dosing day

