- 27) Acute infection requiring systemic anti-infectives, antivirals, or antifungals within two weeks prior to first dose
- 28) Systemic treatment, within 14 days before the first dose of ixazomib, with strong CYP3A inducers (rifampin, rifapentine, rifabutin, carbamazepine, phenytoin, phenobarbital), or use of Ginkgo biloba or St. John's wort.
- 29) Ongoing or active systemic infection, active hepatitis B or C virus infection, or known human immunodeficiency virus (HIV) positive.
- 30) Any serious medical or psychiatric illness that could, in the investigator's opinion, potentially interfere with the completion of treatment according to this protocol.
- 31) Known allergy to any of the study medications, their analogues, or excipients in the various formulations of any agent.

32) Known GI disease or GI procedure that could interfere with the oral absorption or tolerance of ixazomib including difficulty swallowing.
33) Diagnosed or treated for another malignancy within 2 years before study enrollment or previously diagnosed with another malignancy and have any evidence of residual disease. Patients with non-melanoma skin cancer or carcinoma in situ of any type are not excluded if they have undergone complete resection.
34) Patient has \geq Grade 3 peripheral neuropathy or Grade 2 with pain on clinical examination during the screening period.
35) Participation in other clinical trials, with other investigational agents not included in this trial, within 30 days of the start of this trial and throughout the duration of this trial.

Duration of Study:

Subjects will be treated on protocol for 12 months or until disease progression or if lenalidomide and/or ixazomib are permanently discontinued due to intolerance before the end of 1 year. Patients who complete 12 months of protocol treatment will be taken off protocol with management as per PI discretion and standards of care but will continue to be followed for progression, if the patient did not progress on study treatment, and survival.

STUDY OVERVIEW DIAGRAM

SCHEDULE OF EVENTS

Assessment	Screening ²	Cycles 1-12				EOT	Long-term follow-up
		1	8	15	22		
Day	-42 to -1						
Informed Consent+♥	X						
Medical History / Treatment History ¹	X						
Skeletal Survey	X						
ECG ³	X					X	
Physical Exam / ECOG ^{4,5}	X	X				X	
Vital Signs ⁶	X	X				X	
Height ⁷ , Weight, BSA	X	X				X	
24-hour urine ⁸	X	X				X	
Urinalysis	X					X	
C- Reactive Protein	X						
Hematology ⁹	X	X	[X]	[X]		X	

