1.3 Clinical Experience

Ixazomib has been evaluated as an oral single agent in Phase 1 studies that have included patients with advanced solid tumors, lymphoma, relapsed/refractory MM (RRMM), and relapsed or refractory light-chain (AL) amyloidosis, with demonstrated early signs of activity. Ongoing studies continue to investigate both single-agent ixazomib and ixazomib in combination with standard treatments. Based on encouraging preliminary data observed in patients with MM requiring systemic treatment, 2 Phase III trials in newly diagnosed MM (NDMM) (C16014) and RRMM (C16010) patient populations are currently evaluating ixazomib in combination with lenalidomide and Dexamethasone (Rd) versus placebo/R/d. Both trials compare ixazomib at a weekly dose of 4.0 mg on Days 1, 8, and 15 in a 28-day cycle to a standard dose of lenalidomide with a weekly dexamethasone dose of 40 mg. In addition, ongoing clinical pharmacology studies

include evaluation of drug-drug interactions with ketoconazole and rifampin, effect of food, and oral bioavailability. Studies evaluating the safety and pharmacokinetics (PK) of ixazomib alone (in Japanese patients) and in combination with lenalidomide and dexamethasone in Asian adult patients (including Japanese patients) with a diagnosis of NDMM are ongoing.

As of 27 March 2013, preliminary clinical data is available for a total of 653 patients across 13 studies. The emerging safety profile indicates that ixazomib is generally well tolerated. The adverse events (AEs) are consistent with the class-based effects of proteasome inhibition and are similar to what has been previously reported with Velcade though the severity of some, for example peripheral neuropathy, is less. While some of these potential toxicities may be severe, they can be managed by clinical monitoring and standard medical intervention, or, as needed, dose modification or discontinuation.

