Ixazomib is not an inhibitor of Pgp, BCRP, and MRP2. The potential for DDIs with substrates or inhibitors of Pgp, BCRP, and MRP2 is, therefore, inferred to be low. Clinical Study C16009 (Arm 1) with ketoconazole, a strong CYP3A4 inhibitor, showed a 2-fold increase in area under the plasma concentration versus time curve (AUC) in the presence of ketoconazole. This resulted in the continued exclusion of strong CYP3A4 inhibitors in ongoing/planned clinical studies.

Further details on these studies are provided in the IB.

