5.2 Exclusion Criteria

Patients meeting any of the following exclusion criteria are not to be enrolled in the study:

1. Evidence of progressive disease on lenalidomide maintenance as per IMWG criteria
2. Patients who have already started or received multi-drug consolidation regimen post-transplant except for patients receiving up to 6 months of single agent lenalidomide maintenance.
3. Longer than 12 months since the initiation of induction therapy at the time of start lenalidomide maintainance
4. Prior progression after initial therapy.
 - a) Subjects, whose therapy changed due to suboptimal response, intolerance, etc., remain eligible, provided they do not meet criteria for progression.
 - b) No more than two regimens will be allowed excluding dexamethasone alone.
5. Diarrhea > Grade 1 in the absence of anti-diarrheals
6. Central Nervous System involvement of the disease under study.
7. Female patients who are lactating or have a positive serum pregnancy test during the screening period.

8. History of allergy to mannitol
9. Major surgery within 14 days before enrollment.
10. Radiotherapy within 14 days before randomization. If the involved field is small, 7 days will be considered a sufficient interval between treatment and administration of the ixazomib.
11. Evidence of current uncontrolled cardiovascular conditions, including uncontrolled cardiac conditions such as hypertension, or cardiac arrhythmias, or New York Heart Association Stage III and IV congestive heart failure, or unstable angina or myocardial infarction within the past 6 months.
12. Rate-corrected QT interval of electrocardiograph (QTc) > 470 msec on a 12-lead ECG during screening
13. Uncontrolled diabetes
14. Acute infection requiring systemic anti-infectives, antivirals, or antifungals within two weeks prior to first dose
15. Systemic treatment, within 14 days before the first dose of ixazomib, with strong CYP3A inducers (rifampin, rifapentine, rifabutin, carbamazepine, phenytoin, phenobarbital), or use of Ginkgo biloba or St. John's wort.
16. Ongoing or active systemic infection, active hepatitis B or C virus infection, or known human immunodeficiency virus (HIV) positive.
17. Any serious medical or psychiatric illness that could, in the investigator's opinion, potentially interfere with the completion of treatment according to this protocol.
18. Known allergy to any of the study medications, their analogues, or excipients in the various formulations of any agent.

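### Section 1.4 says strong CYP3A4 inhibitors stay excluded, but the lists that sites follow restrict only inducers

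*Combined protocol and SAP*

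**What the plan says.** Section 1.4 (Pharmacokinetics and Drug Metabolism) raises the possibility of interactions with strong inhibitors as well as strong inducers of CYP3A4 or CYP1A2. It then gives one clinical result: in Study C16009, Arm 1, ketoconazole raised the ixazomib AUC 2-fold. The consequence is stated as "This resulted in the continued exclusion of strong CYP3A4 inhibitors in ongoing/planned clinical studies", and the reader is sent elsewhere for more: "Further details on these studies are provided in the IB".

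The eligibility text is narrower. Exclusion 15 in Section 5.2 and item 28 in the Protocol Summary both open with "Systemic treatment, within 14 days before the first dose of ixazomib, with strong CYP3A inducers", list six drugs, and add Ginkgo biloba and St. John's wort.

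The on-study text matches. Section 7.4.2 lists "Strong CYP3A inducers: rifampin, rifapentine, rifabutin, carbamazepine, phenytoin, and phenobarbital" and the same two supplements. It says these drugs "should be avoided, unless there is no appropriate alternative medication". The reason it gives for not being stricter is that with an inducer "ixazomib exposure would be less; therefore, there would be a reduced chance of an AE".

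**The concern.** The protocol describes two directions of interaction. One lowers ixazomib exposure and, on the protocol's own reasoning, makes adverse events less likely. The other doubles exposure. Only the first is restricted in the text that a site uses to screen patients and to approve concomitant drugs.

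A site that follows the lists correctly could therefore start or continue a strong CYP3A4 inhibitor in a patient on ixazomib, with no prompt to look for an alternative, hold a dose or call the Lead Principal Investigator. What is at stake is avoidable toxicity in the experimental arm. The control arm takes lenalidomide alone and is not exposed to this interaction.

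**Working it through.** The plan has no figure of its own to reproduce. The 2-fold AUC is a result cited from another study, and the documents give no data behind it. The check is a comparison of texts.

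**1. Which places restrict what**

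| Place | Strong CYP3A inducers | Strong CYP3A4 inhibitors |
|---|---|---|
| Section 1.4 (background) | named as a possible interaction | 2-fold AUC reported; said to stay excluded in ongoing and planned studies |
| Protocol Summary, item 28 | excluded, 14 days before first ixazomib dose | not mentioned |
| Section 5.2, exclusion 15 | excluded, 14 days before first ixazomib dose | not mentioned |
| Section 7.4.2 | avoided on study unless there is no alternative | not mentioned |
| Sections 7.4.1, 7.4.3, 7.5 (recommended, permitted, precautions) | not mentioned | not mentioned |

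Section 7.4.2 also bars other anticancer and investigational agents and higher-dose corticosteroids. For drugs that alter ixazomib metabolism, its list stops at inducers and the two supplements.

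**2. Whether the stated rationale explains the gap.** Section 7.4.2 tolerates an unavoidable inducer because exposure falls. With an inhibitor, exposure rises, so the same reasoning points the other way. It cannot be the reason that inhibitors are left out.

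**3. What covers some inhibitor use incidentally**
- Exclusion 14: "Acute infection requiring systemic anti-infectives, antivirals, or antifungals within two weeks prior to first dose". This keeps out some users at entry only, and because of the infection rather than the enzyme.
- Exclusion 16: active systemic infection, active hepatitis B or C, or known HIV. Again this acts at entry only.
- Table 7-7: all three drugs are held during systemic treatment of a Grade 3-4 infection. A lower-grade infection, prophylaxis, or a use unrelated to infection is not covered.

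**4. What limits harm once toxicity appears**
- Section 7.3 lets the treating investigator hold ixazomib for treatment-related toxicity.
- Table 7-6 acts on ixazomib directly for neuropathy and for related Grade 3-4 non-hematologic events.
- Section 7.6 provides for restarting at a lower level after rash, thrombocytopenia or neutropenia.
- Table 7-5 lowers lenalidomide first for the first severe within-cycle platelet event and lets ixazomib restart unreduced. Its footnote a allows both to be lowered together.

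These rules are substantial, but they are triggered by toxicity. None asks whether an interacting drug is the cause.

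**5. How far a change would reach**
- Eligibility edit: Version 2.6 is dated 25 Sept 2019, and Section 4.4 ends accrual by 31 March 2020. That is 5 + 31 + 30 + 31 + 31 + 29 + 31 = 188 days at most.
- On-study list: 12 cycles × 28 days = 336 days of planned treatment per patient.

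The on-study list is therefore the more useful place for the change. Neither edit touches the sample size (60), the one-sided 10% type I error or the 80% power.

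**The case against.** The strongest reply is that Section 1.4 is background on the ixazomib programme, not a rule of this trial. It defers to the IB, and the clinical summary beside it is old: "As of 27 March 2013, preliminary clinical data is available for a total of 653 patients across 13 studies". The three operative places agree with each other, and Section 7.4.2 is introduced and justified entirely in terms of inducers. That pattern fits a deliberate inducer-only list beside a sentence nobody updated. This much stands: the documents do not show which text is intended, and the IB that would settle it is not available here. It does not remove the point. No reason for leaving inhibitors out is given, and whichever text is right, the other needs correcting.

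The second reply is that the toxicity rules are broader than a single row of Table 7-5 suggests. That also stands, as step 4 of the working shows. They mitigate; they do not prevent.

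Three stronger readings are tempting and are not supported:
- A reader might infer that a safety restriction was dropped by mistake. The text shows a mismatch, not its cause.
- A reader might double the 3 mg or 4 mg dose and compare it with a maximum tolerated dose in Table 1-1. That needs exposure to be proportional to dose, which the documents do not state.
- A reader might infer that a short inhibitor course would turn a patient into a treatment failure or lock in a lower dose. Section 8.1.4 counts patients who discontinue treatment, not those with a temporary hold. The bar on re-escalation in Section 7.3.1 covers reductions made for toxicity, not a reduction made in advance because of an interaction.

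**Conclusion.** The mismatch is real and the point is minor. On the documents alone, following the lists lets an ixazomib-arm patient take a type of drug that Section 1.4 says doubles ixazomib exposure, at an unchanged dose. Protection is partial and mostly comes after the event.

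The only documented size is the 2-fold AUC with ketoconazole. The frequency of inhibitor use is not given, so no expected number of affected patients can be stated. No effect on the primary endpoint is claimed, and the statistical design is untouched.

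The conclusion that a restriction should be added assumes that the current IB or SMA has not lifted it. If it has, what remains is one outdated background sentence.

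**What to change.** First check the current IB and SMA.

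**Unless they have lifted the restriction:**
1. Add systemic strong CYP3A4 inhibitors to the Section 7.4.2 list, under the avoid-unless-no-alternative wording that already governs inducers.
2. Add them to exclusion 15 and Protocol Summary item 28. Take the washout interval from the IB: the 14 days in the protocol are given for inducers, and nothing in the documents supports that interval for inhibitors.
3. For an unavoidable course, have the site discuss an ixazomib hold or dose change with the Lead Principal Investigator. Section 7.3 already requires this for dose modifications outside the protocol, so no new mechanism is needed.

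**If they have lifted it:** correct the sentence in Section 1.4 and leave the lists alone.

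The cost is the check and a few lines in an amendment, with no new procedures. A few patients may need a different concomitant drug, have ixazomib held briefly, or be ineligible. If a hold is kept within the 21 days that Section 7.3.1 uses for delays, dosing on Days 1, 8 and 15 means that at most 3 doses are missed. With 3 × 12 = 36 planned doses, that is 3/36 = 8.3%.

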7.4.3 Permitted Concomitant Medications and Procedures

The following medications and procedures are permitted during the study:

- Antiemetics, including 5-HT3 serotonin receptor antagonists, may be used at the discretion of the investigator.
- Loperamide or other antidiarrheal should be used for symptomatic diarrhea at discretion of the investigator. The dose and regimen will be according to institutional guidelines. IVF should be given to prevent volume depletion.
- Growth factors (e.g., granulocyte colony stimulating factor [G-CSF], granulocyte macrophage-colony stimulating factor [GM-CSF], recombinant erythropoietin) are permitted. Their use should follow published guidelines and/or institutional practice. Erythropoietin will be allowed in this study. Their use should follow published guidelines and/or institutional practice.
- Patients should be transfused with red cells and platelets as clinically indicated and according to institutional guidelines however screening platelet count must be independent of platelet transfusions for at least 2 weeks.
- Antiviral therapy such as acyclovir may be administered if medically appropriate.
- Concomitant treatment with bisphosphonates will be permitted, as appropriate.
- Patients who experience worsening neuropathy from baseline may be observed for recovery and have dose reductions/delays as indicated in the protocol, and any supportive therapy or intervention may be initiated as appropriate at the discretion of the investigator.
- Supportive measures consistent with optimal patient care may be given throughout the study.

- Radiation therapy to a localized mass is acceptable with prior approval of the Lead Principal Investigator.
- Prophylactic proton pump inhibitor or an H2 antagonist are recommended but NOT required and considered optional medications.
- Vaccines that are required post-transplant.

7.5 Precautions and Restrictions

- Fluid deficit should be corrected before initiation of treatment and during treatment.
- Nonsteroidal anti-inflammatory drugs (NSAIDs) should be avoided with impaired renal function given reported NSAID-induced renal failure in patients with decreased renal function.

Pregnancy

It is not known what effects ixazomib has on human pregnancy or development of the embryo or fetus. The use of lenalidomide in pregnant females and nursing mothers has not been studied nor has the effect of the lenalidomide on human eggs and sperm. Lenalidomide is structurally related to thalidomide. Thalidomide is a known human teratogenic active substance that causes severe life-threatening birth defects. An embryo/fetal development study in animals indicates that lenalidomide produced malformations in the offspring of female monkeys who received the drug during pregnancy. The teratogenic effect of lenalidomide in humans cannot be ruled out. Therefore, a risk minimization plan to prevent pregnancy must be observed.

Female patients participating in this study should avoid becoming pregnant, and male patients should avoid impregnating a female partner. Non-sterilized female patients of reproductive age group and male patients should use effective methods of contraception through defined periods during and after study treatment as specified below.

Female patients must meet 1 of the following:

- Postmenopausal for at least 1 year before the screening visit, or
- Surgically sterile, or

- If they are of childbearing potential, agree to practice 2 effective methods of contraception from the time of signing of the informed consent form through 90 days after the last dose of study drug, or
- Agree to practice true abstinence, when this is in line with the preferred and usual lifestyle of the subject. (Periodic abstinence [e.g., calendar, ovulation, symptothermal, post-ovulation methods] and withdrawal are not acceptable methods of contraception.)

Male patients, even if surgically sterilized (i.e., status post-vasectomy) must agree to 1 of the following:

- Practice effective barrier contraception during the entire study treatment period and through 90 days after the last dose of study drug, or
- Agree to practice true abstinence, when this is in line with the preferred and usual lifestyle of the subject. (Periodic abstinence [e.g., calendar, ovulation, symptothermal, post-ovulation methods for the female partner] and withdrawal are not acceptable methods of contraception.)

All study participants must be registered into the mandatory lenalidomide REMS® program and be willing and able to comply with the requirements of lenalidomide REMS®. Before starting lenalidomide, FCBP must have 2 negative pregnancy tests (sensitivity of at least 50 mIU/mL) prior to initiating lenalidomide. The first pregnancy test must be performed within 10-14 days before, and the second pregnancy test must be performed within 24 hours before prescribing lenalidomide (prescriptions must be filled within 7 days). The subject may not receive lenalidomide until the investigator has verified that the results of these pregnancy tests are negative.

7.6 Management of Clinical Events

Adverse drug reactions such as thrombocytopenia, diarrhea, fatigue, nausea, vomiting, and rash have been associated with ixazomib treatment. Management guidelines regarding these events are outlined below. Further details of management of ixazomib AEs are described in Section 6 of the ixazomib IB.

Prophylaxis Against Risk of Reactivation of Herpes Infection

Patients may be at an increased risk of infection including reactivation of herpes zoster and herpes simplex viruses. Antiviral therapy such as acyclovir, valacyclovir, or other antivirals will be mandatory (see section 7.4.1). Other antivirals are also acceptable.

Nausea and/or Vomiting

Standard anti-emetics including 5-hydroxytryptamine 3 serotonin receptor antagonists are recommended for emesis if it occurs once treatment is initiated; prophylactic anti-emetics may also be considered at the physician's discretion. Dexamethasone should not be administered as an anti-emetic. Fluid deficit should be corrected before initiation of study drug and during treatment.

Diarrhea

Prophylactic antidiarrheals will not be used in this protocol. However, diarrhea should be managed according to clinical practice, including the administration of antidiarrheals once infectious causes are excluded. Fluid intake should be maintained to avoid dehydration. Fluid deficit should be corrected before initiation of treatment and during treatment.

Erythematous Rash With or Without Pruritus

As with bortezomib, rash with or without pruritus has been reported with ixazomib, primarily at the higher doses tested and when given with agents where rash is an overlapping toxicity. The rash may range from limited erythematous areas, macular and/or small papular bumps that may or may not be pruritic over a few areas of the body, to a more generalized eruption that is predominately on the trunk or extremities. Rash has been most commonly characterized as maculopapular or macular. To date, when it does occur, rash is most commonly reported within the first 3 cycles of therapy. The rash is often transient, self-limiting, and is typically Grade 1 to 2 in severity.

Symptomatic measures such as antihistamines or corticosteroids (oral or topical) have been successfully used to manage rash and have been used prophylactically in subsequent cycles. The use of a topical, IV, or oral steroid (e.g., prednisone \leq 10 mg per day or equivalent) is permitted. Management of a Grade 3 rash may require intravenous antihistamines or corticosteroids. Administration of ixazomib (and/or other causative agent if given in combination) should be modified per protocol and re-initiated at a reduced level from where rash was noted (also, per protocol).

In line with clinical practice, dermatology consult and biopsy of Grade 3 or higher rash or any SAE involving rash is recommended. Prophylactic measures should also be considered if a

patient has previously developed a rash (e.g., using a thick, alcohol-free emollient cream on dry areas of the body or oral or topical antihistamines). A rare risk is Stevens – Johnson Syndrome, a severe and potentially life-threatening rash with skin peeling and mouth sores, which should be managed symptomatically according to standard medical practice. Punch biopsies for histopathological analysis are encouraged at the discretion of the investigator.

Thrombocytopenia

Blood counts should be monitored regularly as outlined in the protocol with additional testing obtained according to standard clinical practice. Thrombocytopenia may be severe but has been manageable with platelet transfusions according to standard clinical practice. Ixazomib administration should be modified as noted as per dose modification recommendations in the protocol when thrombocytopenia occurs (see Table 6-2). Therapy can be reinitiated at a reduced level upon recovery of platelet counts. A rare risk is thrombotic thrombocytopenic purpura (TTP), a rare blood disorder where blood clots form in small blood vessels throughout the body characterized by thrombocytopenia, petechiae, fever, or possibly more serious signs and symptoms. TTP should be managed symptomatically according to standard medical practice.

Neutropenia

Blood counts should be monitored regularly as outlined in the protocol with additional testing obtained according to standard clinical practice. Neutropenia may be severe but has been manageable. Growth factor support is not required but may be considered according to standard clinical practice. Ixazomib administration should be modified as noted as per dose modification recommendations in the protocol when neutropenia occurs (see Table 6-2). Therapy can be reinitiated at a reduced level upon recovery of ANC.

Fluid Deficit

Dehydration should be avoided since ixazomib may cause vomiting, diarrhea, and dehydration. Acute renal failure has been reported in patients treated with ixazomib, commonly in the setting of the previously noted gastrointestinal toxicities and dehydration.

Fluid deficit should be corrected before initiation of study drug and as needed during treatment to avoid dehydration.

Hypotension

Symptomatic hypotension and orthostatic hypotension with or without syncope have been reported with ixazomib. Blood pressure should be closely monitored while the patient is on study treatment and fluid deficit should be corrected as needed, especially in the setting of

concomitant symptoms such as nausea, vomiting, diarrhea, or anorexia. Patients taking medications and/or diuretics to manage their blood pressure (for either hypo- or hypertension) should be managed according to standard clinical practice, including considerations for dose adjustments of their concomitant medications during the course of the trial. Fluid deficit should be corrected before initiation of study drug and as needed during treatment to avoid dehydration.

Posterior Reversible Encephalopathy Syndrome

One case of posterior reversible encephalopathy syndrome, which ultimately resolved, has been reported with ixazomib. This condition is characterized by headache, seizures and visual loss, as well as abrupt increase in blood pressure. Diagnosis may be confirmed by magnetic resonance imaging (MRI). If the syndrome is diagnosed or suspected, symptom-directed treatment should be maintained until the condition is reversed by control of hypertension or other instigating factors.

Transverse Myelitis

Transverse myelitis has also been reported with ixazomib. It is not known if ixazomib causes transverse myelitis; however, because it happened to a patient receiving ixazomib, the possibility that ixazomib may have contributed to transverse myelitis cannot be excluded.

